Adverse events assessment (NCI CTCAE V5.0)		x ⁷					x ⁷

1. Monitor vital signs before study drug infusion and at 60±10 minutes after drug infusion started. ECG before study drug infusion and at 2 hours ± 15 min after drug infusion. Body temperature should be recorded daily when in hospital.
2. The complete physical examination should be done during screening. The D15 visit should record any changes.
3. The tests that have been done 72 hr prior to screening are allowed in lieu of screening. See Section 7.1.5 for details.
4. Arterial Blood Gas (ABG) and Chest image study: Chest X-ray or CT scan frequency may be determined by local institutional guideline. The ABG and Chest Image Study at Screening is recommended but not required. The ABG and chest image studies that have been done 72 hr prior to Screening are allowed in lieu of screening.
5. The clinical status (NIAID ordinal scale) and respiratory treatment status should be evaluated and recorded daily while the patient is hospitalized. If the patient is discharged, these data should be captured for study visits through telemedicine.
6. For specified clinical sites only: Blood samples should be collected before and after study drug infusion, and on D4, D8, D15 to measure inflammatory cytokines (IL-1β, IL-6, TNF-α, MIPα, INF-γ, IP10, MCP, GCSF, IL-10) and DAMP molecules (HMGB-1, HSP70 / 90) in serum. The PBMC will be used to measure lymphocyte subtypes and lymphocyte activation and exhaustion markers (flow cytometry for: CD3 / CD4 / CD8 / PD1 / Tim3, etc.).
7. When enrolled patient is in the hospital for the treatment, the study schedule should be followed. If the patient is improved and discharged from the hospital, the follow up visits (D4±2, D8±2, D15±2, D29±3) can be conducted via telephone or video interview for clinical status evaluation, concomitant medications and adverse events assessment. The scheduled laboratory and radiology studies are recommended but not required.

CD24Fc-007-US PROTOCOL SIGNATURE PAGE

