10. STATISTICAL ANALYSIS

10.1. Sample size

In the phase III trial, the patients will be randomized at 1: 1 ratio into CD24Fc or placebo arms. It was assumed that the time to improvement the clinical status of the patients obeyed the exponential distribution, and the improvement hazard ratio (HR) was 1.54. The median time to improvement in the control group is presumed 11 days, and the median time to improvement in the treatment group is projected as 7.14 days. An interim analysis for efficacy will be performed when 70% of the required events are reached. The O'Brien-Fleming type consumption function of the Lan-DeMets algorithm is used to control the overall class I error rate $\alpha = 0.025$ (one-sided), at least 80% of the degree of confidence. At least 208 events are required to achieve 80% power. Assuming 28 days of patient follow up, the estimated number of 208 events will be reached for the final analysis approximately 28 days after the last subject is enrolled. Assuming 78% recovery rate, 270 participants will be enrolled in this trial.

The sample size was calculated on SAS 9.4 PROC SEQDESIGN.

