For the primary endpoint, during the observation period, an improvement from NIAID scale 2, 3 or 4 to scale 5 or above, if sustained without a drop below 5, is considered as an event. The days from the randomization to the first time point of such improvement will be defined as time of improvement. Additional follow-up can be used to determine clinical improvement events.

Subjects who do not withdraw or do not experience improvement will be censored on the actual date of the D29 visit.

Subjects without improvement but lost to follow-up will be censored on the last date of follow-up.

Subjects with death within 28 days will be censored on D29.

Sensitivity analysis:

(1) Imbalances in age, baseline score, use of antiviral drugs such as remdesivir, or IL-6/IL-6R antagonist, or related factors that may affect the results will be investigated with sensitivity analyses and these factors will be evaluated separately in the Cox-Model to assess their potential impact on the primary efficacy endpoint.

(2) Use only data from planned visits to analyze time to improvement in the main analysis.

(3) The days from randomization to the first clinical improvement will be analyzed.

Since there are no available best supportive case (BSC) for this disease, controlling BSC use between two arms is difficult, and consequently there may be imbalance for some particular BSCs between two arms. To evaluate whether there may be some potential bias caused by such imbalance, we will evaluate the percentage of the largest and second largest BSC used in the trial if the difference of such BSC between two arms are significant. Further analyses will be performed to study whether the efficacy results are indeed caused by such differential BSC use between two arms.

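### Sensitivity analysis (2) does not define planned visits; read with the six-visit schedule it dates recovery only at D4, D8, D15 and D29, and the plan's Cox and Kaplan-Meier methods then tend to understate or blur a real effect.

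*Combined protocol and SAP*

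**What the plan says.** Section 10.4.1 dates the primary event at the first clinical status score of 5 or more, or at hospital discharge, whichever is earlier, provided that the improvement is sustained. It names a log-rank test, Kaplan-Meier medians and a Cox model. It adds that additional follow-up may be used to determine events. No method for tied times is given.

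Under the sensitivity heading of the same section, item (2) reads in full: "Use only data from planned visits to analyze time to improvement in the main analysis". The item does not define planned visits, say whether daily scores count, or say how an improvement between two visits is dated.

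On data collection, footnote 5 to Table 2 in the synopsis says: "The clinical status (NIAID ordinal scale) and respiratory treatment status should be evaluated and recorded daily while the patient is hospitalized". After discharge the same footnote moves to capture at study visits by telemedicine. Section 3.1 gives each subject six visits: screening, D1, D4, D8, D15 and D29. Table 2 footnote 7 and Section 7.2.2 put windows of ±2 days on D4, D8 and D15 and ±3 on D29. Section 3.1 has ±1 on D8, ±2 on D15, ±4 on D29 and none on D4.

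Section 10.1 supplies the planning values. Controls are taken to have a median of 11 days. For CD24Fc the section says: "the median time to improvement in the treatment group is projected as 7.14 days".

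**The concern.** A robustness check is useful if it agrees with the primary result when that result is sound. Item (2), read with the six-visit schedule, replaces daily dating by four post-dose dates, which fall 3, 7, 14 and 28 days after randomization on D1. A patient who improves on day 8 after randomization is dated day 14; one who improves on day 15 is dated day 28. The recovery time is then known only to an interval of up to two weeks, yet the Kaplan-Meier and Cox methods of Section 10.4.1 treat it as exact. At nominal dates nearly all events are tied, and the Cox estimate then depends on a tie method that the plan does not name.

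At stake is the interpretation of the trial. A true effect of the planned size could be followed by a check showing a smaller hazard ratio and no difference in medians, and be called fragile for reasons that come from the grid. The open wording also leaves the definition of planned visits, the dating rule and the tie method to be chosen after the data are seen.

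**Working it through.** **Inputs (Section 10.1).** Exponential times, control median 11 days, CD24Fc median 7.14 days; "the improvement hazard ratio (HR) was 1.54"; 135 per arm; 28 days of follow-up. Visit times are 3, 7, 14 and 28 days. Assumed: no deaths, relapses or losses, and, for the windowed case, visit dates spread uniformly within ±2 days (±3 at D29).

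**The plan's own figures.** 11/1.54 = 7.14 and 11 − 7.14 = 3.86 days, so the planned medians and their difference reproduce. 208/0.78 = 267, close to 270. The 208 events do not reproduce from a one-sided 0.025 and 80% power: 4(1.960 + 0.842)²/(ln 1.54)² gives 169, or 171 with the look at 70%. That is a separate matter, and 208 is not used below.

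**Step 1: improvement by each visit.** F(t) = 1 − 2^(−t/median).

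| Day | Control | CD24Fc |
|---|---|---|
| 7 | 35.7% | 49.3% |
| 14 | 58.6% | 74.3% |
| 28 | 82.9% | 93.4% |

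**Step 2: median difference at nominal dates.** With 135 per arm the Kaplan-Meier median is the first visit by which at least 68 have improved. From the binomial distribution:
- Control reads 14 days with probability 0.978 and 28 days with probability 0.022.
- CD24Fc reads 7 days with probability 0.437 and 14 days with probability 0.563.
- P(difference 0) = 0.978 × 0.563 = 0.551.
- P(difference 7) = 0.978 × 0.437 = 0.427.
- P(difference 14 or 21) = 0.022.

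So 0 or 7 appears in 0.551 + 0.427 = 0.978 of trials. With dates spread in the windows, the difference takes most whole-day values from 0 to 8, mean 4.0. Daily dating gives a mean of 3.8.

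**Step 3: hazard ratio and power.** From 1,500 simulated trials, true value 1.54:

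| Dating | Cox, Breslow | Cox, Efron | Log-rank power |
|---|---|---|---|
| Daily | 1.52 | 1.54 | 92% |
| Visits, nominal dates | 1.39 | 1.52 | 90% |
| Visits, dates in windows | 1.44 | 1.48 | 85% |

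The 92% is in line with the expected events: 135 × (0.829 + 0.934) = 238, and Φ(√238/2 × ln 1.54 − 1.96) = 0.915.

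**Step 4: the plan's 78% recovery rate.** The exponential medians imply 238/270 = 88% recovered by day 28, not 78%. A model with the control median kept at 11 days, a hazard ratio of 1.54 and 78% overall recovery (its form is an assumption) gives:
- Hazard ratio, Breslow and Efron: 1.43 and 1.53 at nominal dates; 1.49 and 1.52 in windows; 1.52 and 1.54 daily.
- Median difference at nominal dates: 0 in 26% of trials, 7 in 67%.
- Log-rank power: 88% daily, 88% nominal, 85% windowed.

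**Step 5: a model suited to the grid.** Under proportional hazards, the ratio of log survival between arms is the hazard ratio in every interval. At day 7 it is ln(1 − 0.4932)/ln(1 − 0.3567) = 0.680/0.441 = 1.54. A complementary log-log model with one intercept per visit estimates this quantity. It gave 1.54 in the nominal-date simulation. A fresh large-sample run (40,000 per arm) gave 1.55 at both nominal and windowed dates, against 1.55 on daily data with Efron ties in the same sample.

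**The case against.** **Item (2) may not discard the daily scores.** Section 10.4.1 allows additional follow-up to determine events, so a planned-data-only check could be meant to remove just that. Daily in-hospital scores are themselves scheduled in Table 2. On that reading daily dating stays and the figures above do not apply. This stands as a possibility. Against it, Section 3.1 counts six visits, footnote 5 speaks of study visits separately from daily recording, and the narrower meaning is nowhere stated.

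**A reader might infer that the median difference can only read 0 or 7 days.** The documents do not support that. It needs nominal dates, and even then about 2% of trials read 14 or 21. Section 10.4.1 computes time from dates, and the visits have windows.

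**A reader might infer that the hazard ratio is always pulled well towards 1.** That is also too strong. With Efron ties at nominal dates the loss is about 0.02. It is material with Breslow ties, which the plan neither names nor excludes, and moderate with either method when actual dates vary in the windows. Under the 78% recovery model it is smaller throughout.

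**A reader might take the closing words of item (2) as restricting the primary analysis.** The item stands under the sensitivity heading, and Section 10.4.1 fixes the primary dating by daily score or discharge. The words are a drafting fault, not a change to the primary test.

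**Little depends on the item.** It carries no alpha and no decision rule, and items (1) and (3) and Section 10.6 give other checks. This limits the weight of the point.

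**Conclusion.** The point holds as a cheap improvement to a supportive analysis. On the ordinary reading of item (2), and with the plan's exponential medians, a true hazard ratio of 1.54 is reported as about 1.39 to 1.52 at nominal dates and 1.44 to 1.48 with dates spread in the windows, against 1.52 to 1.54 on daily data. At nominal dates the median difference reads zero in about 55% of trials, or about 26% under an assumed 78% recovery model, although the planned difference is 3.86 days. Log-rank power on visit data is 90% or 85% against 92%.

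These sizes rest on the coarse reading of planned visits, on proportional hazards, on the assumed uniform spread within windows, and on ignoring deaths, relapses and losses. The primary log-rank test and its event dating are not affected.

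**What to change.** 1. Delete the closing four words of item (2), so that it cannot be read as a rule for the primary analysis.
2. State which analysis is meant. Either planned visits are D4, D8, D15 and D29 and daily scores and discharge dates between visits are not used; or only unscheduled follow-up is removed and daily dating is kept.
3. If visit-only data are meant, replace the item with wording such as: *Planned-visit data (D4, D8, D15, D29) will be analysed as interval-censored, using a discrete-time complementary log-log proportional hazards model with one intercept per visit. Its hazard ratio will be compared with the primary hazard ratio. A difference in medians on the visit grid will not be interpreted.*
4. Reconcile the visit windows in Section 3.1 with those in Table 2 footnote 7 and Section 7.2.2, since they decide which scores belong to a planned visit.

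Cost: a few sentences and one standard model, with no new data. The downside is a supportive analysis without a median. The change should be made before unblinding.

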10.4.2. Secondary efficacy endpoints

Proportion of death or respiratory failure, defined as the need for mechanical ventilation, ECMO, non-invasive ventilation, or high flow oxygen devices at D29. Cumulative number of subjects reaching the composite endpoint vs number of people in the ITT population. Chi-square test will be used to compare the difference between the two arms.

For the disease progression, during the observation period, a progression from scale 3 or 4 to scale 2 or 1, or from 2 to 1, is considered as an event. The days from the randomization to the first time point of progression will be defined as time of progression. The probability function of clinical progression will be estimated by Kaplan-Meier method. The median time and its 95% confidence interval for each group will be reported. The 95% confidence interval for the median time will be estimated using the Brookmeyer-Crowley method with log-log function conversion to achieve a normal approximation. The progression rate will be estimated by the layered Cox-Model. Cumulative progression rates estimated by the KM method for day 29 and the 95% confidence intervals will be reported.

All-cause mortality at Day 15 and Day 29: the Mantel-Haenszel stratum-weighted estimator of the risk difference will be used to compare the treatments.

Rate of clinical relapse, defined as proportion of patients who have initially reached score 5 (hospitalized, without oxygen therapy) for more than one day but subsequently become dependent on oxygen support. Since responders are not based on the randomization, a descriptive statistic will be reported and an exploratory analysis using a Chi-square test will be performed.

Improvement rate of clinical status on Days 8 and 15 (proportion of subjects with clinical improvement): percentage of subjects with clinical improvement on Day 8 or 15 in the ITT population. Chi-square test will be used to compare the difference between the two arms.

The discharge time starts from randomization to discharge. T-tests will be used to compare the differences between the two groups in completers.

Duration of each major treatment (days): Descriptive statistics will be analyzed for mechanical ventilation (IMV, NIV), extracorporeal membrane oxygenation, duration of oxygen therapy, and length of hospital stay.

Absolute Lymphocyte Count: patients' dynamic changes in absolute lymphocyte count during the treatment / observation period will be monitored to assess the possible correlation between lymphocyte levels and disease outcome and prognosis.

D-dimer levels: patients' dynamic changes in D-dimer levels during the treatment / observation period will be monitored to assess the possible correlation between lymphocyte levels and disease outcome and prognosis.

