Study Design:	
The study is designed as a randomized, placebo-controlled, double blind, multicenter, Phase III trial to compare two COVID-19 treatment regimens in hospitalized adult subjects who are diagnosed with severe COVID-19.
 
Arm A: CD24Fc/Best Available Treatment Arm B: placebo/ Best Available Treatment
 
CD24Fc will be administered as single dose of 480 mg via IV infusion on Day 1. Total of 270 subjects will be enrolled and randomized in 1:1 ratio to receive CD24Fc or placebo. All subjects will be treated with the best available treatment. The follow up period is 28 days.
 
If the patient clinical status improves and is discharged to home care, the follow up visits can be carried out through telemedicine (phone or video interviews). The clinical investigators should make best effort to obtain the vital signs, clinical status evaluation, concomitant medicines and adverse events assessment. The laboratory tests, radiology study, ECG and research samples are optional.

Primary Objective:	The primary objective of the Phase III study is to evaluate the safety and efficacy of adding CD24Fc to COVID-19 best available treatment by comparing COVID disease status improvement time between CD24Fc and placebo arms in 28 days.
Secondary Objectives:	Secondary objectives are to compare, for each treatment arm, the proportion of patients who died or had respiratory failure (defined as the need for mechanical ventilation, ECMO, non-invasive ventilation, or high flow oxygen devices), the time to disease progression, the rate of all-cause death, the proportion of death or respiratory failure, rates of hospital discharge time, rate of duration of mechanical ventilation, duration of mechanical ventilation, use of pressors, rate of duration of extracorporeal membrane oxygenation, rate of duration of supplemental oxygen, the length of hospital stay, and the changes in absolute lymphocyte count and markers of inflammation.
Exploratory objectives:	
To explore the effect of CD24Fc treatment of COVID-19 on systemic steroid dosage, inflammatory cytokine changes, D-dimer level changes, lymphocyte subtype distribution and T lymphocyte activation and exhaustion markers.
 
To explore the effect of CD24Fc in pulmonary function, inflammatory markers, coagulation markers, cardiac function, liver enzymes and renal function.

Study Endpoints:

Primary Endpoint:

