Time to improvement in clinical status: the time (days) to the improvement of clinical status from “scale 2 to 4” to “scale 5 or above that is sustained without a drop to below 5” based on NIAID 8-point ordinal scales ([Appendix A](#)) within 28 days from randomization.

Secondary Endpoints:

- Proportion of patients who died or had respiratory failure, defined as the need for mechanical ventilation, ECMO, non-invasive ventilation, or high flow oxygen devices, at Day 29;
- Time to disease progression in clinical status: the time (days) for progression from scale 3 or 4 to scale 1 or 2, or 2 to 1, based on NIAID ordinal scale with 28 days from randomization;
- All-cause mortality at Day 15 and Day 29;
- Proportion of clinical relapse, as defined by rate of return to oxygen support for more than 1 day within 28 days from randomization after initial recovery;
- Conversion rate of clinical status on days 8 (proportion of subjects who changed from “scale 2 to 4” to “scale 5 or higher” on NIAID ordinal scale);
- Conversion rate of clinical status on days 15 (proportion of subjects who changed from “scale 2 to 4” to “scale 5 or higher” on NIAID ordinal scale);
- The discharge time
- Duration of mechanical ventilation (IMV, NIV) (days);
- Duration of pressors;
- Duration of extracorporeal membrane oxygenation (days);
- Duration of oxygen therapy (oxygen inhalation by nasal cannula or mask) (days);
- Length of hospital stay (days);
- Absolute lymphocyte count;
- D-dimer concentration in the plasma.

Exploratory endpoints:

- Effect of CD24Fc on systemic steroid usage;
- Effect of CD24Fc on cytokine levels;
- Effect of CD24Fc on lymphocyte subtype distribution.

Safety evaluation:

- Adverse events, vital signs, laboratory tests (blood routine, blood biochemistry, coagulation function, urine routine), ECG.

Study Population:

Hospitalized severe and critical COVID-19 adult patients.

Eligibility Criteria:

Inclusion criteria

- 1) Should be at least 18 years of age.

- 2) Male or female, female should have negative pregnancy test.
- 3) Diagnosed with COVID-19 and confirmed SARS-CoV-2 viral infection, prior positive viral results allowed.
- 4) Informed consent form signed by the patient or by the legally authorized representative.
- 5) Hospitalized and requiring oxygen support, NIAID 8-point ordinal score 2, 3 or 4, regardless of ARDS ([Appendix A](#)). The intubation for mechanical ventilation is within 7 days.

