2. STUDY OBJECTIVES

2.1. Primary objective:

- To evaluate the safety and efficacy of adding CD24Fc to COVID-19 best available treatment by comparing COVID-19 disease status improvement time between CD24Fc and placebo arms within 28 days.

2.2. Secondary objectives:

- Secondary objectives are to compare, for each treatment arm, proportion of patients who died or had respiratory failure (defined as the need for mechanical ventilation, ECMO, non-invasive ventilation, or high flow oxygen devices), the time to disease progression, rate of all-cause death, proportion of death or respiratory failure, rates of hospital discharge time, rate of duration of mechanical ventilation, duration of mechanical ventilation, use of pressors, rate of duration of extracorporeal membrane oxygenation, rate of duration of supplemental oxygen, the length of hospital stay, and the changes in absolute lymphocyte count and markers of inflammation.

2.3. Exploratory objectives:

- To explore the effect of CD24Fc treatment of COVID-19 on systemic steroid dosage, inflammatory cytokine changes, D-dimer level changes, lymphocyte subtype distribution and T lymphocyte activation and exhaustion markers.
- To explore the effect of CD24Fc in pulmonary function, inflammatory markers, cardiac function, liver enzymes and renal function.

2.4. Primary Endpoints:

- Time to improvement in clinical status: the time (days) required for improvement from scale 2 - 4 to scale ≥ 5 or above that is sustained without a drop to below 5 based on NIAID ordinal scales ([Appendix A](#)) within 28 days from randomization.

2.5. Secondary Endpoints:

- Proportion of patients who died or had respiratory failure, defined as the need for mechanical ventilation, ECMO, non-invasive ventilation, or high flow oxygen devices, at Day 29
- Time to disease progression in clinical status: the time (days) for progression from scale 3 or 4 to scale 1 or 2 based on the NIAID ordinal scale within 28 days from randomization.
- All cause mortality at Day 15 and Day 29
- Proportion of clinical relapse, as defined by rate of return to oxygen support for more than 1 day within 28 days from randomization after initial recovery

- Conversion rate of clinical status on Day 8 (proportion of subjects who changed from “scale 2, 3 or 4” to “scale 5 or higher” in the NIAID ordinal scale)

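### Death or respiratory failure is timed at Day 29 but counted cumulatively over ITT, with no rule for patients who enter already on scale 2–3 support

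*Combined protocol and SAP*

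**What the plan says.** In section 10.4.2 the composite is death or need for mechanical ventilation, ECMO, "non-invasive ventilation, or high flow oxygen devices at D29". The next sentence gives the numerator and denominator: "Cumulative number of subjects reaching the composite endpoint vs number of people in the ITT population". The arms are then compared by chi-square test.

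The endpoint lists carry the Day 29 timing and say nothing about cumulative counting: "or high flow oxygen devices, at Day 29" in the Synopsis and "non-invasive ventilation, or high flow oxygen devices, at Day 29" in section 2.5.

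The objectives give no time point. The Synopsis names the composite twice, first as "the proportion of patients who died or had respiratory failure" and again within "the rate of all-cause death, the proportion of death or respiratory failure, rates of hospital discharge time". Section 2.2 does the same, its second mention reading "rate of all-cause death, proportion of death or respiratory failure, rates of hospital discharge time".

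Section 4.1 admits patients at NIAID score 2, 3 or 4. Under Appendix A, scores 2 and 3 are invasive ventilation or ECMO, and non-invasive ventilation or high-flow oxygen. These are the supports that define respiratory failure in this endpoint.

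The next paragraph of 10.4.2 does give progression a baseline rule: "a progression from scale 3 or 4 to scale 2 or 1, or from 2 to 1, is considered as an event". The composite has no such rule. Section 10.3.1 defers detail to a statistical analysis plan, but the supplied text contains no further counting rule.

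**The concern.** A proportion with an event at Day 29 can mean status on that day or any occurrence up to that day. The plan uses the first kind of wording for the endpoint and the second for the count. Neither reading can be applied safely as written. Under the first, the counting sentence measures something else. Under the second, a cumulative ITT count takes in patients who met the failure definition before treatment could act, and their later course cannot change their classification.

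At stake is the estimate and test for one secondary endpoint. Table 2 (footnote 5) has status and respiratory support recorded daily in hospital and at study visits after discharge, so both versions can be computed. If the text stays as it is, the choice between them could be made after results are known.

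**Working it through.** **The two rules on single patients**

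| Patient | Status on Day 29 | Cumulative through Day 29 |
|---|---|---|
| Enters at scale 4, intubated Day 5, home by Day 20 | no event | event |
| Enters at scale 3, improves, home by Day 20 | no event | event from entry, if entry support counts |

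The first row needs no assumption about baseline handling. The second arises from the eligibility criteria.

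**Inputs**

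- N = 270, 135 per arm (section 3.2).
- Required events 208 and assumed recovery 78% (section 10.1).
- f, the share on scale 2–3 support when counting starts: not in the documents. Assumed 20, 30, 50 and 70%.

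The plan gives no event rate, effect size or power for this endpoint, so there is no figure of its own to reproduce. The sample-size figures used here do agree with each other: 208 / 0.78 = 266.7, against 270 planned.

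**Ceiling on Day-29 status events**

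Recovery in section 10.4.1 is improvement to scale 5 or above, sustained. A recovered patient is therefore neither dead nor at scale 2–3 on Day 29. Without loss to follow-up:

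maximum events by Day-29 status = 270 × (1 − 0.78) = 59.4, about 59 of 270 (22%).

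This is an upper limit, because patients still at scale 4 are also unrecovered.

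**Floor on the cumulative count with entry support included**

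minimum events = 270f. The two proportions must differ when 270f > 59.4, that is, when f > 0.22.

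| Assumed f | Minimum cumulative events (270f) | Per arm (135f) | Day-29 status ceiling | Forced to differ? |
|---|---|---|---|---|
| 20% | 54 | 27 | 59 | no |
| 30% | 81 | 40.5 | 59 | yes |
| 50% | 135 | 67.5 | 59 | yes |
| 70% | 189 | 94.5 | 59 | yes |

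Below 22% the rules can still disagree, through failures that resolve, but these figures do not force it.

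**Effect on the arm difference**

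Let e_C and e_T be the cumulative risks among scale-4 entrants, with f the same in both arms in expectation under randomization. With entry support counted, the arm proportions are f + (1 − f)e_C and f + (1 − f)e_T. Their difference is (1 − f)(e_C − e_T).

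For f = 30, 50 and 70% the factor is 0.7, 0.5 and 0.3, whatever the event rates. Any drug effect in scale 2–3 entrants contributes nothing.

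**The case against.** The best defence is that the Day 29 timing simply means by Day 29, and that the counting sentence is the operational rule. Section 10.4.2 supports this: it uses Day 29 wording for all-cause mortality and for the Kaplan–Meier cumulative progression rate, both of which accumulate over time. The objectives, with no time point, also fit a cumulative count. This may well be the intended meaning. A reader might infer that the section flatly contradicts itself; the documents do not support that, because a consistent reading exists.

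What the defence does not do is make the rule sound. Read as cumulative over ITT, with no from-to provision, it counts scale 2–3 entrants as events from entry. So one reading leaves an inconsistency and the other leaves a dilution.

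It is also fair to say that the consequence is limited. The chi-square test is valid for two ITT proportions. Nothing in the plan ranks this endpoint above the other secondary endpoints or allocates alpha to it. Site personnel are blinded until database lock (section 11.9.1). A choice made after seeing results is possible, but nothing shows that it is planned or likely.

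**Conclusion.** The point holds as a defect in the counting rule of one secondary endpoint. Either the count does not match the stated timing, or it includes entry support and shrinks the scale-4 difference by (1 − f). The (1 − f) factor needs no event rates, only equal f in the arms in expectation. The 22% threshold rests on the 78% recovery assumption and no loss to follow-up. The actual size depends on f, which the documents do not give.

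Three stronger conclusions are tempting and not supported:

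- **That the rule favours the drug.** It does not. The same expected share f is added to both arms, which dilutes the difference.
- **That Day-29 status is the better or more powerful rule.** The documents do not show this. Each rule loses something, and which gives the larger difference depends on event rates that the plan does not state.
- **That a power loss can be quoted.** The plan supplies no rates for this endpoint, and any assumed pooled Day-29 rate above 22% would conflict with its own recovery assumption. No power figure is offered here.

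The primary endpoint, Day 8 and 15 improvement, progression and mortality analyses are unaffected. The point should be fixed because the remedy is cheap and the rule as written can give a misleading estimate.

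**What to change.** State one rule before unblinding, and use the same wording in the Synopsis objectives and endpoints, sections 2.2 and 2.5, and section 10.4.2. Either would do:

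- **(a) Status rule.** Dead by Day 29, or at NIAID scale 2–3 at the Day 29 assessment, over all ITT subjects in the arm.
- **(b) Cumulative rule.** Any new event after randomization through Day 29, with an explicit from-to rule for scale 2–3 entrants like the one already written for progression.

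Report the version not chosen as supportive.

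Compare the arms stratified by baseline score, which section 7.1.12 already requires at screening. The Mantel–Haenszel risk difference that 10.4.2 uses for mortality would serve, with the strata named. Expect only a small gain; the fix does not depend on it.

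Each choice has a downside. Rule (a) misses failures that resolve before Day 29. It also needs a line on which assessment counts as Day 29 (the visit window is ±4 days in section 3.1 and ±3 in Table 2 and section 7.2.2, to be reconciled) and on how a missing score is classified, since section 10.6 gives only time-to-event rules. Rule (b) cannot register persisting failure in scale 2–3 entrants unless the from-to rule covers it.

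The cost is a few sentences and one supportive table. No new data are needed.
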